3.3.2 Primary Endpoint Analysis

The data will be entered in a Microsoft Excel spreadsheet for analysis. The statistician assigned will analyze the data to determine statistical significance between conditions if present.

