Study Protocol and Statistical Analysis Plan

Clinical Study of Released Unitron RIC and
BTE Hearing Aid Models – ID# 515

January 4, 2022.

NCT05197803

Clinical Study of Released Unitron RIC and BTE Hearing Aid Models – ID# 515

1 Objectives and hypotheses of the clinical investigation

1.1 Purpose of the clinical investigation claims for clinical performance, effectiveness or safety of the investigational device that are to be verified

This clinical study intends to show that compared to the unaided condition, the released Unitron RIC and BTE hearing aid models provide amplification that will improve speech intelligibility when programmed for individual hearing losses. The study (and the resulting clinical data) will support the clinical benefit claim: “improved speech understanding” necessary to update the CER which is necessary for the CE submission. The claim will not be use externally or in any marketing material.

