3.1 Determination of Sample Size

Although we have no prior data showing an estimated mean difference between unaided and aided conditions, we looked at the literature to estimate aided vs unaided benefit.

Valente & Mispagel (2008) investigated unaided and aided (Omni and Directional) HINT performance in adults with a sloping normal to moderately-severe SNHL. Results had shown that aided-directional HINT performance was significantly better than both unaided or aided-omni

conditions. The mean difference (1.7 dB) and SD (2.4) between unaided and aided-directional performance were used for the power analysis and ultimately calculating sample size.

Power Analysis was done using the G*Power Software (Faul et al., 2007). Power analysis was done for a one-tailed dependent t-test between two means. The table below list the input parameters used to calculate sample size.

Input parameters	Output parameters

• Mean of differences: 1.7• SD of differences: 2.4• Effect size dz: 0.708• Alpha=0.05• Power=0.95	
• Non centrality parameter: 3.40• Critical t: 1.72• Actual power: 0.95• Df: 22• Total sample size: 23

Based on the above calculations, it was determined that a minimum of 23 participants will be required based on a power analysis using arms-length data.

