3.3 Planned Analysis

The data analysis will be done upon completion of data collection. A one-tailed t-test will be done as part of the analysis.

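### Does the primary analysis need a stricter alpha and a planned confidence interval before it can support the benefit claim?

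*Combined protocol and SAP*

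**What the plan says.** Section 1.1 states that the study data "will support the clinical benefit claim" of better speech understanding, for the clinical evaluation and CE file. It also rules out external or marketing use of the claim. The objective in section 1.2 is directional: to confirm that hearing-aid use improves HINT performance in noise.

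Section 3.1 sizes the study. It reads "Power analysis was done for a one-tailed dependent t-test between two means", with "Mean of differences: 1.7", "SD of differences: 2.4", alpha 0.05 and power 0.95, and arrives at 23 participants.

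The analysis text is brief. Section 3.3 says "A one-tailed t-test will be done as part of the analysis". Section 3.3.1 lists two comparisons, unaided against RIC and unaided against BTE, in 20 to 25 participants. Section 3.3.2 says "The statistician assigned will analyze the data to determine statistical significance between conditions if present". None of these sections states an alpha, an estimate of benefit, an interval or a smallest worthwhile gain.

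**The concern.** The study calls itself confirmatory and feeds a regulatory file, yet the only result it names is significant or not significant. One-tailed 0.05 corresponds to two-sided 0.10, which many reviewers would find lenient for a single confirmatory study. A reader given only a p-value could not tell a gain of 0.9 dB from one of 1.7 dB. Improvement could also be declared when the customary two-sided 95% interval includes zero. If so, the benefit claim would rest on a small gain of unstated precision.

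**Working it through.** **Inputs, all from section 3.1:** mean paired difference 1.7 dB, SD 2.4 dB, one-tailed alpha 0.05, n = 23. Applying that alpha to the analysis is an inference, because sections 3.3 to 3.3.2 give none.

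**The plan's own figure.**
- dz = 1.7 / 2.4 = 0.708, matching "Effect size dz: 0.708".
- Noncentrality = 0.7083 × √23 = 3.397.
- The one-sided critical t on 22 df is 1.717, matching "Critical t: 1.72".
- Exact noncentral-t power is 0.950 at n = 23 and 0.942 at n = 22, so 23 is the minimum. The sample size reproduces.

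**Smallest significant observed gain.**
- SE = 2.4 / √23 = 0.500 dB.
- One-sided 0.05: 1.717 × 0.5004 = 0.859 dB, and 0.859 / 1.7 = 51%.
- One-sided 0.025: 2.074 × 0.5004 = 1.038 dB, and 1.038 / 1.7 = 61%.
- At the 0.859 dB threshold the two-sided 95% interval is 0.859 ± 1.038, or −0.18 to 1.90 dB.
- Over the permitted sample sizes, the one-sided 0.05 threshold is 0.93 dB (55%) at n = 20 and 0.82 dB (48%) at n = 25.
- With n = 23 and an assumed SD of 2.0 or 3.0 dB, it is 0.72 dB (42%) or 1.07 dB (63%).

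**Why about half.** The ratio of threshold to planned effect is (critical t × SD/√n) / (dz × SD) = critical t / noncentrality = 1.717 / 3.397 = 0.51. It is fixed by the choice of alpha and power and says nothing particular about this trial. A stricter level barely moves it if power is held: at one-sided 0.025 and n = 28, 2.052 / 3.748 = 0.55. The 0.86 dB is also an observed mean, not a true effect. If the true gain were half the planned one (0.85 dB), power at n = 23 would be about 0.50.

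**How often the two levels disagree.** The result must fall between t = 1.717 and t = 2.074.
- Under the planning assumptions: 0.950 − 0.901 = 0.049 per comparison.
- Under no benefit: 0.050 − 0.025 = 0.025 per comparison.

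**Price of the stricter level.**

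| n | Power, one-sided 0.05 | Power, one-sided 0.025 |
|---|---|---|
| 20 | 0.920 | 0.852 |
| 23 | 0.950 | 0.901 |
| 25 | 0.964 | 0.925 |
| 28 | 0.978 | 0.951 |

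Keeping 0.95 at one-sided 0.025 needs 28 participants, above the planned 20 to 25.

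**Recovering the interval.** A paired t-test is computed from the mean difference and its SE, so the interval needs no further data. If 1.7 dB were observed with t = 3.397, then SE = 1.7 / 3.397 = 0.500 and the 95% interval is 1.7 ± 2.074 × 0.5004, or 0.66 to 2.74 dB.

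**The case for a change.** The best case for a change is that what is permitted is not prespecified. Nothing obliges the sponsor to report an estimate or interval, section 3.3.3 plans no secondary analysis that could supply one, and the analysis sections set no alpha. One sentence in section 3.3.2 would close the gap, with no new data and no loss of power if the one-tailed level stays.

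The factual part of this stands: the estimate, interval and analysis alpha are absent, and reporting them would be good practice. It does not show that the plan goes wrong. Section 3.3 describes the t-test as one part of the analysis, so estimates are unplanned, not excluded. Section 3.1 gives the only alpha, sidedness and pairing in the document, and an analyst would carry them over.

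The argument for a stricter alpha is weaker. It rests on convention from outside the document, and requiring a 95% interval above zero would still confirm at 1.04 dB. Nor does the claim require 1.7 dB to be shown. That figure is a literature value used for planning, and the claim is qualitative, so a test against zero fits it.

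**Conclusion.** The concern does not call for a change. Followed as written, the plan gives a valid one-tailed paired test of whether each form factor improves HINT performance, at the level and power used to size the study. Adding an interval would not alter that test's conclusion. Replacing the level with one-sided 0.025 is a trade-off: at n = 23 it halves the nominal false-positive rate per comparison, from 0.05 to 0.025, and lowers power from 0.95 to 0.90. The sponsor chose a one-tailed test in advance and applied it consistently.

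What remains is unwritten reporting detail that a competent analyst would supply from the same calculation. The conclusion assumes that the analysis uses the paired, one-tailed 0.05 test of section 3.1. The dB figures also assume an SD near 2.4 dB, which comes from another study; the ratio of about one half at the planned effect and power does not depend on the units.

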3.3.3 Secondary Endpoint Analysis

Non applicable.

4 Informed consent process

4.1 Process for obtaining informed consent

Participants are required to sign a consent form prior to participation in the study. The consent form will be provided at the time of their first appointment and relevant tick boxes for this particular study will be noted. Participants will consent by writing their names and signature and will include the name of the researcher obtaining consent. The document will be converted into a PDF and will be uploaded into the database. The paper forms will be stored in a secured cabinet only accessible by the researchers.
